11.4.3.3. Clinical Laboratory Evaluation Analyses

Descriptive statistics will be provided for the clinical laboratory results by scheduled time of evaluation and by treatment arm for the Safety Analysis Set, as well as for the change from baseline. The baseline value is defined as the last non-missing value before the initial administration of study drug. In addition, mean change from baseline will be presented by treatment arm for the maximum and minimum post-treatment values and the values at the Discontinuation Visit.

Shift tables (in categories of low, normal, and high) will be provided for each treatment arm for selected clinical laboratory parameters. Also, the number and percentage of subjects with clinically relevant abnormal clinical laboratory values while on study drug will be calculated for each treatment arm for selected clinical laboratory parameters. All abnormal clinical laboratory values will be presented in a listing. Specifically, the number and percentage of subjects with elevation of liver enzymes (ALT, AST) and TBL, according to various multiples of ULN will be summarized by treatment arm. The number and percentage of subjects with concurrent elevation of ALT or AST $\geq 3 \times$ ULN and TBL $\geq 2 \times$ ULN will also be summarized by treatment arm.

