8. PHARMACOKINETIC/PHARMACODYNAMIC ASSESSMENTS

Approximately, the first 12 subjects of each age cohort (total of approximately 53 to 60 subjects) randomized to the edoxaban treatment arm will participate in the multiple-dose PK/PD assessment ([Table 8.1](#)) on Day 5 (+3 days, Visit 2a) as follows (subject number is determined by evaluable blood specimens demonstrating edoxaban exposure):

- Ages 12 to <18 years (N≈12)
- Ages 6 to <12 years (N≈12)
- Ages 2 to <6 years (N≈12)
- Ages 6 months to <2 years (N≈12)
- Ages birth to <6 months (N≈5-12)

Blood samples will be collected on the day of the fifth dose of edoxaban (Day 5+3 days, Visit 2a) for all age cohorts, including:

- PK pre-dose sample.
- PK post-dose sample can be taken at either:
 - any time between 1.0 to 3 hours post-dose
 - or
 - any time between 5 to 8 hours post-dose
- The PD sampling times on Day 5 for measurement of PT, aPTT and anti-FXa, will be taken at the same time as the PK samples.
- A PK analysis will be performed on subjects in U312 study. If the analysis of the subjects confirms the exposure predictions and based on emerging safety, the expanded enrollment in the same age cohort will be allowed to start. A notification will be sent to all Investigators that expansion of the age cohort is permitted after the PK analysis. In addition, a notification will be sent indicating that recruitment for Day 5 edoxaban-treated subjects will no longer be necessary for that particular cohort.
- One blood sample will be drawn for RFT (serum creatinine and blood urea nitrogen) on or around Day 5 (at the same time of PK sampling).

Enrollment in the next younger age cohorts in U312 study will begin upon the availability of:

- PK analysis performed on subjects in the prior older age cohort in U312.
- Safety data analysis on subjects in the prior older age cohort in U312.
- PK analysis of the subjects in the next younger age cohort in U157.
- Safety data analysis on the subjects of the next younger age cohort in U157.

PK and safety data will be reviewed by an IDMC ([Section 15.9](#)) who will approve the start of the next younger age cohort.

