9.8.2. Blood chemistry

A serum separating tube of blood will be drawn for the blood chemistry assessments listed in Table 9.2. These will be measured from samples obtained at the Screening /Qualification Visit (Visit 1). For the Screening /Qualification visit, samples taken as part of routine care may be analyzed by local laboratories. The results may be used to qualify the subject, provided the tests were performed for the newly diagnosed index VTE before randomization. If central laboratory is also used at the same visit with a resulting discrepancy for exclusion criteria, the local laboratory result will still be used to qualify the subject.

Creatinine will also be measured on Month 1, 3, 6, 9, and Month 12 / Discontinuation Visits.

Table 9.2: Blood Chemistry

Sodium	Creatinine ^a
Potassium	Blood urea nitrogen
Bicarbonate	Alkaline phosphatase

AST	Total bilirubin
ALT	

^a Serum creatinine will be measured at Screening, On-Treatment Study Visits (Month 1, 3, 6, 9 and Month 12/ Discontinuation)

Abbreviations: ALT = alanine aminotransferase; AST = aspartate aminotransferase

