11.2. General Statistical Considerations

All efficacy analyses will be based on the mITT Analysis Set or PP Analysis Set and will be performed based on the treatment arm assigned at randomization. All statistical tests will be two-sided at a 5% significance level, unless otherwise specified.

Safety analysis will be performed using the Safety Analysis Set. Subjects will be analyzed according to actual treatment received.

Unless otherwise specified, the baseline value of an efficacy variable for a subject is the last non-missing measurement before the first administration of study drug, and the baseline value of a safety variable is the last non-missing measurement before the first dose of the study drug.

In general, missing data will not be imputed for the purpose of data analysis. No visit windows will be used for analysis.

Continuous variables will be summarized by the number of observations, mean, standard deviation, median, and minimum and maximum values. Categorical variables will be summarized using frequency counts and percentages. Summary statistics will be presented by treatment arm.

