17. APPENDICES

17.1. Schedule of Events

Table 17.1: Schedule of Events

Study Period	Screening/ Qualification Visit	Randomization ^a	On-Treatment Study Visits								Required 30 Day Follow- Up Visit ^b
			Main Treatment Period				Extension Period (Optional)				
Visit Number	1	2	2a	3	4	5	6	7	8	9	
Study Day	At least Day-5 to -1 Index VTE Event Identified Pre-randomization treatment selected by PI (LMWH or SP Xa inhibitor or UFH)	Day 1 1 st EDX Dose	Day 5 EDX arm only N=53 to 60	Month 1	Month 2	Month 3	Month 6	Month 9	Month 12/ Discontinuation Visit		
Visit Window (Days) ^c			+3	±5	±5	±5	±5	±5	±5	±5	±5
IXRS transaction	X										
IXRS Randomization		X									
Study Informed Consent	X										
Confirm Diagnosis of Index VTE	X										
Inclusion/Exclusion Criteria	X										
Demographic Information	X										
Medical/Surgical History	X										

Table 17.1: Schedule of Events (Continued)

Study Period	Screening/ Qualification Visit	Randomization ^a	On-Treatment Study Visits								Required 30 Day Follow- Up Visit ^b
			Main Treatment Period				Extension Period (Optional)				
Visit Number	1	2	2a	3	4	5	6	7	8	9	
Study Day	At least Day-5 to -1 Index VTE Event Identified Pre-randomization treatment selected by PI (LMWH or SP Xa inhibitor or UFH)	Day 1 1 st EDX Dose	Day 5 EDX arm only N=53 to 60	Month 1	Month 2	Month 3	Month 6	Month 9	Month 12/ Discontinuation Visit		
Physical Examination and Body Height/Weight Assessments ^d	X			X	X	X	X	X	X		

Table 17.1: Schedule of Events (Continued)

Study Period	Screening/ Qualification Visit	Randomization ^a	On-Treatment Study Visits								Required 30 Day Follow- Up Visit ^b
			Main Treatment Period				Extension Period (Optional)				
Visit Number	1	2	2a	3	4	5	6	7	8	9	
Study Day	At least Day-5 to -1 Index VTE Event Identified Pre-randomization treatment selected by PI (LMWH or SP Xa inhibitor or UFH)	Day 1 1 st EDX Dose	Day 5 EDX arm only N=53 to 60	Month 1	Month 2	Month 3	Month 6	Month 9	Month 12/ Discontinuation Visit		
Vital Signs ^c	X			X	X	X	X	X	X		
Liver function assessment (ALT, AST, TBL, ALP)	X**			X		X		X	X		
Serum Creatinine	X**		X ^o	X		X	X	X	X		
Serum Chemistry Panel excluding creatinine	X**		X ^o								
Screening only: INR Measurement on VKA and aPTT	X										
Post-randomization: INR, Anti-FXa, aPTT, assessment on SOC ^{f,g}			X		
Hematology	X**						X			X	

Table 17.1: Schedule of Events (Continued)

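### The edoxaban-only Day 5 renal test slightly biases the by-arm creatinine extremes and leaves BUN with no SOC comparator

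*Combined protocol and SAP*

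**What the plan says.** Section 11.4.3.3 plans several by-arm laboratory summaries. One uses each subject's extremes: "mean change from baseline will be presented by treatment arm for the maximum and minimum post-treatment values". Another, for selected parameters that are not named, counts "the number and percentage of subjects with clinically relevant abnormal clinical laboratory values while on study drug". Neither is restricted to visits scheduled in both arms. The same section also plans a summary by visit: "Descriptive statistics will be provided for the clinical laboratory results by scheduled time of evaluation and by treatment arm".

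Table 17.1 heads the Visit 2a column "Day 5 EDX arm only N=53 to 60"; SOC has no such visit. Section 8 places a renal sample there: "One blood sample will be drawn for RFT (serum creatinine and blood urea nitrogen) on or around Day 5". Footnote o of Table 17.1 likewise calls the Day 5 chemistry entries a renal function test. Neither place states an age limit. Section 6.3.1.1 gives the test to Cohort 5 and singles out infants aged 28 days or less.

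For both arms, Section 9.8.2 states: "Creatinine will also be measured on Month 1, 3, 6, 9, and Month 12 / Discontinuation Visits". It gives no repeat of the rest of the chemistry panel after screening, and Table 17.1 marks that row only at screening and Day 5.

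**The concern.** The expected maximum of several measurements grows with their number, the expected minimum falls, and the chance of at least one abnormal value rises. If one arm is measured once more than the other, a by-arm table of extremes differs even when the drugs have identical effects. Here the extra creatinine look falls only on edoxaban. Renal function is a covariate of interest for this drug, so a by-arm creatinine table is likely to be read as a safety signal, and part of any excess would come from the sampling schedule.

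BUN has a different problem. SOC has no scheduled value after screening, so a by-arm maximum, minimum or abnormal count for BUN would set edoxaban Day 5 data against nothing planned.

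**Working it through.** **Inputs.** Arm size is 137 (274 at 1:1, Section 11.6). The Day 5 subset is 4 cohorts x 12 plus 5 to 12 in Cohort 5, which reproduces the plan's 53 to 60. Creatinine looks scheduled in both arms are 2 in the main period (Months 1 and 3) and up to 5 through Month 12. The documents give neither the per-look abnormal rate q nor the within-subject correlation, so both are assumed and varied. I take post-treatment to mean after the first dose, because baseline is defined as the last value before it. Day 5 therefore counts as post-treatment, and it is also on study drug.

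**Mean maximum, independent standard normal looks.** E[max of 2] = 1/√π = 0.564. E[max of 3] = 3/(2√π) = 0.846. The gain is 0.282 SD in a subject who has Day 5. Over the arm, multiply by n/137, where n is the number tested. The minimum moves down by the same amount.

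**Any abnormal value.** The risk is 1 − (1 − q)² with two looks and 1 − (1 − q)³ with three. At q = 5% these are 9.75% and 14.26%, a difference of 4.51 points per tested subject. Over the arm, multiply again by n/137.

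| Tested, n | Excess points, q = 1% | q = 2.5% | q = 5% | Mean maximum |
|---|---|---|---|---|
| 5 | 0.04 | 0.09 | 0.16 | +0.010 SD |
| 12 | 0.09 | 0.21 | 0.40 | +0.025 SD |
| 53 | 0.38 | 0.92 | 1.75 | +0.109 SD |
| 60 | 0.43 | 1.04 | 1.98 | +0.124 SD |

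At q = 5% the expected number of extra subjects flagged is 0.0451 x n: 0.2 to 0.5 of a subject for n = 5 to 12, and 2.4 to 2.7 subjects for n = 53 to 60.

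**Correlated looks.** The gain in the maximum scales by √(1 − ρ): 0.20 SD at ρ = 0.5 and 0.13 SD at ρ = 0.8. For n = 53 to 60 that is 0.08 to 0.09 SD and about 0.05 to 0.06 SD over the arm. By simulation at q = 5%, the excess of any abnormal value falls to 1.2 to 1.35 points (ρ = 0.5) and 0.7 to 0.8 points (ρ = 0.8).

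**Twelve months, 5 versus 6 looks, independent.** The expected maximum is 1.163 versus 1.267 SD, a gain of 0.104 SD, or 0.040 to 0.046 SD over the arm for n = 53 to 60. At q = 5% the risks are 22.6% and 26.5%, giving 1.5 to 1.7 points over the arm.

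**Where chance alone may understate it.** Appendix 17.7 gives mean normal eGFR of 41 at 1 week, 66 at 2 to 8 weeks and 96 after 8 weeks. In the youngest infants an early creatinine would tend to be the subject's highest post-baseline value, so exchangeable looks may be too mild an assumption in that small group.

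**Which analytes.** Section 8 defines the Day 5 renal sample as creatinine and BUN. Table 17.1 has separate rows for liver function and hematology, and neither is marked at Day 5.

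**The case against.** The best defence is that the effect is too small to matter. Section 6.3.1.1 ties the test to Cohort 5, and the summary of changes also describes Day 5 renal monitoring as a Cohort 5 measure. On that reading at most 5 to 12 of 137 subjects are affected, and fewer if only infants aged 28 days or less are meant. The tables are descriptive, with no test or decision rule. The by-visit summary is free of this bias, and abnormal values are listed in any case. Creatinine is not named among the selected parameters. Section 11.7 leaves detail to a SAP still to be finalized.

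Most of this stands, and it sets the size. It does not remove the defect. The maximum/minimum summary is not limited to selected parameters, so creatinine enters it, and the by-visit table does not correct a table of extremes. Section 8 and footnote o carry no age limit, so the wider count cannot be excluded from the text.

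A reader might infer that liver tests are affected too, because Table 17.1 marks the chemistry-panel row at Day 5 and Table 9.2 lists liver enzymes under blood chemistry. The documents do not support this: that cell carries footnote o, which speaks of renal function only, Section 8 names two analytes, and the liver row has no Day 5 mark. Nor does the lack of analysis visit windows in Section 11.2 add to the problem, since windows do not determine a maximum taken over all values.

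**Conclusion.** The point holds for renal chemistry only. As written, Section 11.4.3.3 gives edoxaban a more extreme expected maximum and minimum creatinine with no true difference. It also gives more chance abnormalities if creatinine is a selected parameter. BUN cannot be compared between arms on scheduled data.

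Under 2 versus 3 independent looks and q = 5%, the arm-level excess is 0.2 to 0.4 points with Cohort 5 alone and 1.7 to 2.0 points (0.11 to 0.12 SD in the mean maximum) with all PK subjects. It is smaller with correlated looks or over 12 months.

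A reader might take from the wider count that edoxaban would show about a fifth more subjects with an abnormal value: 11.50/9.75 = 1.18 to 11.73/9.75 = 1.20. That needs every PK subject to be tested, which the documents leave unsettled. With 5 to 12 subjects the ratio is about 1.02 to 1.04 (9.91/9.75 to 10.15/9.75). A reader might also suppose that dose reductions are affected. They follow an individual subject's eGFR, not these tables. The primary analysis and sample size are untouched.

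**What to change.** In Section 11.4.3.3, or in the SAP that carries it out:

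- Leave creatinine and BUN measured at Visit 2a out of the by-arm maximum/minimum change and the by-arm counts of clinically relevant abnormal values. Keep unscheduled values in both arms.
- Show Visit 2a renal results in a separate edoxaban-only table and keep them in the listing of abnormal values.
- State that no by-arm comparison of post-baseline BUN is planned.
- Reconcile Section 6.3.1.1, Section 8, and the Visit 2a entries and footnote o of Table 17.1 on who has the Day 5 renal test and which analytes it covers.

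The exclusion should go no further than Visit 2a. Limiting these tables to common scheduled visits would also drop unscheduled values, including the repeat and weekly liver tests of Section 5.6.3, where peaks may occur.

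The cost is a few sentences and one visit filter in the laboratory programs. The downside is that Day 5 renal abnormalities appear outside the arm comparison.

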11.4.3.4. Vital Sign Analyses

Descriptive statistics will be provided for the vital signs measurements by scheduled time of evaluation and by treatment arm for the Safety Analysis Set, as well as for the change from baseline. The baseline value is defined as the last non-missing value before the initial administration of study drug.

11.4.3.5. Physical Examination Analyses

A listing of physical examination data will also be provided.

11.4.3.6. Other Analysis

Any additional exploratory analysis will be specified in the SAP.

11.5. Interim Analyses

An interim assessment of incidence rate of the composite efficacy endpoint in both treatment arms of the study will take place after first 140 subjects (about 50% of subjects) complete the first 3 months of treatment. This will allow for adjustment of number of subjects in the study if necessary. Because the sample size re-estimation will be based on overall event rate acrossing two treatment arms, no type I error adjustment is needed for this interim analysis. The detailed interim analysis will be specified in interim SAP (IASAP).

11.5.1. Independent Data Monitoring Committee

An Independent Data Monitoring Committee will monitor the safety data throughout the study and inform the Study Steering Committee on fixed intervals and will be detailed in DMC charter.

11.6. Sample Size Determination

This is an event driven trial and the total number of subjects randomized to treatment may be adjusted to ensure accumulation of 68 events in the mITT Analysis Set during the Main Treatment Period.

The sample size calculation is based on statistical approach and results of Hokusai VTE study (DU176b-D-U305), a study of LMWH/edoxaban versus LMWH/warfarin in the treatment of acute VTE in adults. An NI margin of 1.5 (in hazard ratio) is used in the Hokusai VTE study and was aimed at preserving 70% of warfarin effect in adult population. A hazard ratio of 0.76 of recurrent VTE between edoxaban and warfarin for the first 3 months is also observed in Hokusai VTE study.

This pediatric study is designed to accumulate, approximately 68 overall primary efficacy events in the mITT Analysis Set during the Main Treatment Period. Assuming that edoxaban group will observe a 24% relative reduction to SOC arm, a total of 68 events will give approximately a power of 80% to demonstrate that LMWH/edoxaban is non-inferior to the comparator, considering a relative non-inferiority margin for the hazard ratio of 1.5 (two-sided $\alpha=0.05$).

Based on the completed clinical trials and literature review^{4, 14, 15, 16, 19, 22, 23, 24, 25}, we expect an incidence of composite primary efficacy endpoint of 28% in the control arm during the Main Treatment Period. Based on these estimates, 274 subjects (137 each arm) are expected to be randomized to study drug in order to accrue 68 primary efficacy events in the mITT Analysis Set during the Main Treatment Period.

11.7. Statistical Analysis Process

The data analysis will be performed by a CRO under the guidance of the study biostatistician.

The SAP will provide the statistical methods and definitions for the analysis of the efficacy and safety data, as well as describe the approaches to be taken for summarizing other clinical study information such as subject disposition, demographic and baseline characteristics, study drug exposure, and prior and concomitant medications. The SAP will also include a description of how missing, unused, and spurious data will be addressed.

To preserve the integrity of the statistical analysis and clinical study conclusions, the SAP will be finalized prior to database lock.

All statistical analyses will be performed using SAS® Version 9.2 or higher.

12. DATA INTEGRITY AND QUALITY ASSURANCE

12.1. Monitoring and Inspections

The sponsor or designee's monitor and regulatory authority inspectors are responsible for contacting and visiting the Investigator for the purpose of inspecting the facilities and, upon request, inspecting the various records of the study (eg, CRFs, source data, and other pertinent documents).

The verification of adherence to the protocol; completeness, accuracy, and consistency of the data; and adherence to ICH GCP and local regulations on the conduct of clinical research will be accomplished through a combination of onsite visits by the monitor and review of study data remotely. The frequency of the monitoring visit will vary based on the activity at each study site. The monitor is responsible for inspecting the CRFs and ensuring completeness of the study essential documents. The monitor should have access to subject medical records and other study-related records needed to verify the entries on the CRFs. Detailed information is provided in the monitoring plan.

The monitor will communicate deviations from the protocol, SOPs, GCP and applicable regulations to the Investigator and will ensure that appropriate action (s) designed to prevent recurrence of the detected deviations is taken and documented.

The Investigator agrees to cooperate with the monitor to ensure that any problems detected in the course of these monitoring visits are addressed to the satisfaction of the sponsor and documented.

In accordance with ICH GCP and the Sponsor's audit plans, this study may be selected for audit by representatives from the Sponsor. Audit of study center facilities (eg, pharmacy, drug storage areas, laboratories) and review of study related records will occur in order to evaluate the study conduct and compliance with the protocol, ICH GCP, and applicable regulatory requirements. The Investigator should respond to audit findings. In the event that a regulatory authority informs the Investigator that it intends to conduct an inspection, the Sponsor shall be notified immediately.

12.2. Data Collection

This study employs electronic data capture. The eCRF should be kept current to enable the monitor to review the subject's status throughout the course of the study. The eCRF will be completed, reviewed, and electronically signed by the Investigator. Guidelines will be provided to facilitate data entry in the electronic data capture modules.

All written information, study notes, and other material to be used by subjects and investigative staff must use vocabulary and language that are clearly understood as source documentation.

12.3. Data Management

Each subject will be identified in the database by a unique subject identifier as defined by the sponsor.

To ensure the quality of clinical data across all subjects and study centers, a Clinical Data Management review will be performed on subject data according to specifications given by the sponsor or designee's. Data will be vetted both electronically and manually for CRFs and the data will be electronically vetted by programmed data rules within the application. Queries generated by rules and raised by reviewers will be generated within the EDC application. During this review, subject data will be checked for consistency, completeness and any apparent discrepancies.

Data received from external sources such as central laboratories will be reconciled to the clinical database.

Serious Adverse Events in the clinical database will be reconciled with the safety database.

All medical history entries (except terms pre-specified on the eCRF) and adverse events will be coded using MedDRA. All prior and concomitant medications will be coded using WHO Drug Dictionary.

